7.5 Definition of Visit Windows

Visit windows for all the assessments are displayed in [Table 1](#).

Table 1. Visit Window

Scheduled Visit	Nominal study Rx Day	Time Window (Study Rx Day Range)
Baseline	≤ -1	-21 to -1 days
Week 1 Day 1	1	1 to 8 days
Week 3 Day 1	15	9 to 22 days
Week 5 Day 1	29	23 to 36 days
...
Week (2*X - 1) Day 1	14*X - 13	14*X - 19 to 14*X - 6 days

8.0 Demographics, Baseline Characteristics, Medical History and Previous/Concomitant Medications

Demographic and baseline characteristics, medical history, and prior/concomitant medications will be summarized by treatment groups using the safety population by treatment groups and in overall study population.

8.1 Demographic and Baseline Characteristics

The following demographic, current disease history and baseline disease characteristics will be summarized descriptively.

Demographic Variable	Baseline Disease Characteristics

 • Age • Weight • BMI • Sex • Race (White, Black or African American, Asian, American Indian or Alaskan Native, Native Hawaiian or Pacific Islander) • Ethnicity (Hispanic or Latino, Not Hispanic or Latino) • History of tobacco product use and alcohol use (current, former, never, unknown) 	
 • Histology (Glioblastoma, Gliosarcoma, Other) • Level of neurological function (worse than minor neurofunction impairment, no worse) • MGMT methylation status (methylated, unmethylated, indeterminate) • EGFRvIII status (mutated or other). • Karnofsky performance status (KPS)
	
Baseline Disease Status
 
 • Time since diagnostic GBM surgery to start of study treatment • Type of surgery (Gross total resection, partial resection, biopsy)

8.2 Medical and Surgical History

Medical and surgical history data will be summarized and presented using body systems and conditions/diagnoses (e.g., fatigue, gait disturbance) as captured on the eCRF. The body systems will be presented in alphabetical order and the conditions/diagnoses will be presented in alphabetical order within each body system. The number and percentage of subjects will be summarized for each condition/diagnosis per arm. Subjects reporting more than one condition/diagnosis within a body system will be counted only once for that body system.

8.3 Prior/Concomitant Medications (Excluding Protocol-Required Prophylactic Eye Drops)

Prior medications are any medications excluding the protocol-required prophylactic eye treatment taken after screening visit and prior to the first dose of study drug. Concomitant medications are any medications excluding eye drops, other than study drug, taken after the first dose of study drug and within 49 days of the last dose of study drug, regardless of the start and stop date. Medications taken on the day of the first dose of study drug are counted as concomitant medications.

Prior and concomitant medications will be summarized separately by the generic name coded by the World Health Organization (WHO) dictionary. Subjects reporting the same medication generic name two or more times will be counted only once for that generic name. Subjects reporting more than one medication will be counted only once in the total number of subjects taking a concomitant medication.

8.4 Prior/Concomitant Medications (Protocol-Required Prophylactic Eye Drops)

Concomitant use of eye drops from screening will be summarized by generic name for ophthalmic steroids and Vasoconstrictor eye drops and Cold compress, separately. Listing of eye-drops used will be provided along with dosing information, start date, end date and investigator assessed compliance.

9.0 Subject Disposition and Study Drug Exposure

9.1 Subject Disposition

Subject disposition summary will be presented for all screened subjects by investigator site and overall. The following information will be presented: subjects screened, subjects randomized, subjects who received at least 1 dose of study drug, subjects who received prophylactic treatment, subjects who entered adjuvant phase, and subjects discontinued from the study. In addition, a subject disposition summary will be presented by prophylactic treatment group and overall, including the following information.

- Subjects randomized
 - i. Subjects did not receive any prophylactic treatment
 - ii. Subjects received randomized prophylactic treatment
 - iii. Subjects received treatment different from randomized prophylactic treatment
- Subjects entered in adjuvant phase
- Subjects entered in survival follow-up phase
- Reason for discontinuation from study

In addition, reason for study drug discontinuations will be summarized by treatment arms.

9.2 Study Drug Exposure

Treatment duration for Depatux-M and TMZ are defined as below:

Treatment duration for Depatux-M (in days) = last Depatux-M dose date – first Depatux-M dose date + 15.

Treatment duration for TMZ (in days) = last TMZ dose date – first TMZ dose date + 1.

Exposure to Depatux-M and TMZ will be summarized for chemoradiation phase, adjuvant phase and overall study. Following information will be summarized:

- Overall treatment duration for Depatux-M and TMZ, separately
- Percentage of patients received cumulative dose of RT < 57 Gy, 57 - 63 Gy, > 63 Gy
- Cumulative doses (mg/kg) of Depatux-M and total dose (mg) of TMZ in chemoradiation phase, separately
- Cumulative doses (mg/kg) of Depatux-M and total dose (mg) of TMZ in adjuvant phase, separately
- Cumulative doses (mg/kg) of Depatux-M and total dose (mg) of TMZ in overall study (i.e., combining the chemoradiation and adjuvant phase), separately
- Number of cycles of Depatux-M and TMZ in adjuvant phase, separately

10.0 Efficacy Analysis

No efficacy endpoints will be analyzed in the study.

11.0 Safety Analysis

11.1 General Considerations

Safety analyses will be carried out on Safety population. Categorical safety endpoints (e.g., incidence of AEs, incidence of potentially clinically significant laboratory values) will be summarized using frequencies and percentages.

11.2 Analysis of Primary Endpoint

The proportion of patients who met the primary endpoint defined as (a) either $\geq +0.3$ change on LogMAR scale in baseline adjusted visual acuity or (b) incidence of \geq Grade 3 Corneal Epithelial Adverse Event (CEAE, CMQ: 80000184), anytime over 8 weeks after initiation of Depatux-M and prior to BCL intervention will be summarized by treatment arms and in overall population. This analysis will also be repeated for the Post-BCL intervention period. For the Post-BCL intervention period, analysis will be

limited to the patients who received BCL intervention and baseline will be re-set to the last assessment prior to start of BCL intervention.

Time to the first occurrence (onset) of any CEAE will be assessed using Kaplan Meier methodology and median time to first onset of any corneal AE (along with 95% CI). This analysis will be repeated for Grade 3 or higher corneal AEs.

Time to onset will be measured in days relative to the date of first dose date to the start date of the first occurrence of CEAE. If a subject has not experienced an CEAE, the subject will be censored on the subject's last assessment date (i.e., the day of the subject's last known laboratory assessment, last known vital sign assessment, last known physical exam, last known ocular exam, last known tumor assessment, or last known follow-up visit, whichever is the latest) or 49 days from the subject's last treatment (Depatux-M), whichever is earliest. If the subject has no post-baseline assessment, the data will be censored on the day of first dosing date.

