3.15 Corneal Epithelial Adverse Event Assessment

Corneal epithelial adverse events (CEAEs) will be monitored on a regular basis from initiation of study treatment until symptom resolution after deparatuzumab mafodotin discontinuation, as specified in [Section 2.1](#) and [Section 2.2](#), using the CEAE rating scale and recorded using the CEAE electronic case report form (eCRF; [Appendix H](#)). The CEAE rating scale is designed to describe the overall severity symptoms associated with ADC-related corneal epitheliopathy under a single CEAE grade, while capturing additional information about specific domains (ocular discomfort, photophobia, and blurred vision/visual acuity) that are commonly affected.

It is designed for routine use by the treating physician based on subject reporting without a requirement for formal eye examination, with the exception that a finding of corneal ulceration with impending perforation (CU) or corneal perforation (CP) would be diagnosed on examination by an eye care specialist. To maximize collection of CEAE assessments according to the study schedule, particularly to assess reversibility of OSEs after drug discontinuation, the CEAE assessment may be conducted by telephone and may incorporate information from caregivers.

For the current study symptoms related to the corneal epithelium will be recorded in this eCRF and should NOT be recorded as adverse events in the standard adverse event log.

CEAE Grade (Overall Severity of symptoms/findings related to corneal epithelial abnormalities):

- Only the impact of corneal epithelial abnormalities should be considered in evaluating the CEAE grade.
 - These symptoms generally include blurred vision (decreased visual acuity), photophobia, and ocular discomfort (various terms may be used to describe ocular discomfort).
- If visual ADL impairment is caused primarily by a condition unrelated to the corneal epithelium (e.g., central nervous system [CNS] lesion, retina, lens, optic nerve, etc.), this field should be recorded as "Not evaluable."
- Examples of Instrumental ADLs include preparing meals, shopping for groceries or clothes, using the telephone, managing money, etc.
- Examples of self-care ADLs include bathing, dressing and undressing, feeding self, using the toilet, taking medications, and not bedridden.

Ocular Discomfort

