4.3 Expected Adverse Events

Corneal Epithelial Adverse Events

For adverse events related to corneal epithelial abnormalities, associated signs and symptoms will be recorded and graded by the study investigator using the Corneal Epithelial Adverse Event eCRF, which was created by AbbVie, based on experience with ADC-related corneal epitheliopathy caused by depatuxizumab mafodotin, to address inadequacies of the CTCAE system for appropriately capturing symptoms, grading, and making dose modifications for ADC-related corneal epitheliopathy. Grading of corneal epithelial events is based on effects on visual ADL, as shown in Table 2 of the study protocol, and the eCRF is detailed in [Appendix H](#).

Events recorded in the Corneal Epithelial Adverse Event eCRF events will **not** be recorded in standard adverse event eCRFs, with the exception of a CEAE finding of CU/CP. A CEAE CU/CP would be considered a serious adverse event and would be reported as such as described below.

For eye disorders that are unrelated to corneal epithelial abnormalities (related to lens, retina, etc.), events will be reported as adverse event per usual practice using standard eCRFs and graded according to CTCAE criteria.

Deaths

Deaths that occur during the protocol-specified AE reporting period that are attributed by the investigator solely to progression of GBM should be recorded only on the study completion eCRF with disease progression as the reason for discontinuation and not on the AE eCRF. All other on-study deaths, regardless of relationship to study drug, must be recorded on the AE eCRF and immediately reported to the sponsor.

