5.3 Endpoints

5.3.1 Primary Endpoint

The primary endpoint is defined as the percentage of subjects with either a ≥ 3 -line decline from baseline ($\geq +0.3$ on LogMAR scale) (Bailey IL, Lovie-Kitchin, 2013) in

visual acuity (with baseline correction determined at the screening ophthalmology visit) or \geq Grade 3 OSE severity on the Corneal Epithelial Adverse Event (CEAE) scale, either of which will indicate inadequate control of OSEs requiring a change in OSE management strategy. The primary endpoint is assessed over 8 weeks after initiation of depatuxizumab mafodotin treatment regardless of phases.

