11.4 Analysis of Adverse Events

Treatment Emergent Adverse events (TEAEs) are defined as any AE with onset or increased severity after the first dose of study drug (RT/TMZ/Depatux-M) and no more than 49 days after the last dose of Depatux-M. All AE will be coded according to Medical Dictionary for Regulatory Activities (MedDRA) version 22.0 or higher.

Adverse Event Overview: The summary of subjects experiencing TEAEs by treatment arms will be summarized for the following adverse event categories.

- Any TEAE
- Any TEAE possibly related to Depatux-M
- Any TEAE with CTCAE grade 3 or higher
- Any Grade 3 or higher TEAE possibly related to Depatux-M
- Any TE serious AE (SAE)
- Any TEAE leading to discontinuation of Depatux-M
- Any treatment emergent CEAE
- Any treatment emergent CEAE with CTCAE grade 3 or higher
- Any treatment emergent CEAE leading to discontinuation of Depatux-M
- Deaths (within 49 days from last dose and after 49 days from last dose)

Summary of Adverse Event: Following summary of AE would be produced:

	Regardless of Any Relationship	Relationship to Depatux-M
Any AE (by PT in the descending order)	X	
Any Grade 3 or higher AE (by PT in the descending order of difference in incidence)	X	
Any AE (by SOC and PT)	X	
Any AE (by SOC, PT and Grade)	X	
Grade 3 or higher (by SOC and PT)	X	
SAE (by SOC and PT)	X	X
Leading to ABT-414 discontinuation (by SOC and PT)	X	X
Summary of CEAE (by SOC and PT)	X	
CEAE by highest grade for subjects (by SOC and PT)	X	
Leading to ABT-414 discontinuation (by SOC and PT)	X	

Listings of Adverse Event: The following listings of adverse events will be prepared.

- Listing of treatment-emergent serious adverse events.
- Listing of treatment-emergent AE that led to discontinuation of study drug.
- Listing of treatment-emergent fatal adverse events.
- Listing of Grade 3 or higher adverse events

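### SAP 11.2 and 11.4 find and grade corneal epithelial events by a CMQ, CTCAE grade and SOC/PT, although sites record and grade them on the CEAE eCRF and keep them off the AE log

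*SAP*

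**What the plan says.** **Definition.** SAP 5.3.1 sets the second primary component, called (b) in SAP 11.2, at or above "Grade 3 OSE severity on the Corneal Epithelial Adverse Event (CEAE) scale". Protocol 3.2 and 7.4 use the same scale.

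**Analysis.** SAP 11.2 implements it as "Grade 3 Corneal Epithelial Adverse Event (CEAE, CMQ: 80000184), anytime over 8 weeks after initiation of Depatux-M", restricted to the time before bandage contact lens (BCL) intervention. The same section adds a time-to-first-CEAE analysis that runs to "the start date of the first occurrence of CEAE", and then states: "This analysis will be repeated for Grade 3 or higher corneal AEs". SAP 11.4 lists "Any treatment emergent CEAE with CTCAE grade 3 or higher" in the AE overview and plans a "Summary of CEAE (by SOC and PT").

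**Data collection.** Operations Manual 3.15 says that corneal symptoms go on the CEAE eCRF and "should NOT be recorded as adverse events in the standard adverse event log". Section 4.3 repeats that such events will not "be recorded in standard adverse event eCRFs, with the exception of a CEAE finding of CU/CP" (corneal ulceration with impending perforation, or perforation). Section 4.4 exempts them from CTCAE grading, as do Protocol 6.1 and 6.3. The overall grade, 0 to 5 by effect on visual activities of daily living, is an item on the form in Operations Manual Appendix H.

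**The concern.** The definition points to one data source and the analysis rule appears to point to another. SAP 11.3 names the CRF page that supplies the BCL start date, but no section of the SAP names the CEAE eCRF, or any dataset, as the source of the CEAE grade. A programmer who follows 11.2 and 11.4 literally would look for MedDRA-coded terms with a CTCAE grade. Sites were told not to create such records for these events.

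At stake are component (b) of the primary endpoint before BCL, its repeat after BCL, the two time-to-CEAE analyses, and the CEAE rows of the AE tables. Two SAP outputs could also disagree. A subject given BCL because of a form grade of 3 or 4, without acuity loss, is an event in the SAP 11.3 time-to-event analysis, which counts BCL start as an event. In SAP 11.2, which does not count BCL start, that subject would be a non-event if the form grade were not read. Yet the subject had exactly the change of management that the primary objective is meant to estimate.

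**Working it through.** **1. The texts side by side.**

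| Question | SAP definition (5.3.1) | SAP analysis (11.2, 11.4) | Data collection (Protocol 6.1; Operations Manual 3.15, 4.3, 4.4, Appendix H) |
|---|---|---|---|
| How is the event found? | CEAE scale | CMQ 80000184; tables by SOC and PT | CEAE eCRF; off the AE log except CU/CP |
| How is it graded? | CEAE scale | 11.2 gives a grade without restating the scale; 11.4 says CTCAE | CEAE grade 0 to 5; CTCAE does not apply |
| Which form is the source? | Not named | Not named | CEAE eCRF |

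The CTCAE wording in 11.4 contradicts the Operations Manual outright. The CMQ wording in 11.2 conflicts with it if the query searches AE-log terms. That reading is an inference: neither document defines CMQ. It is supported by 11.4, which codes all AEs in MedDRA and tabulates CEAEs by SOC and PT.

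**2. What a query on the AE log alone would find.** If sites follow the instructions, the log holds CU/CP (Grade 5) and nothing else from the CEAE scale. Component (b) would miss Grades 3 and 4. Time to any CEAE would miss Grades 1 to 4, and those subjects would be censored.

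**3. Size.** The plan gives no figure on this point. Its only figures for the primary endpoint are the precision intervals in Protocol Table 6. These reproduce as Wald intervals: for 12/30, 0.400 ± 1.96 × √(0.4 × 0.6 / 30) = 0.400 ± 0.175, or 22.5% to 57.5%, as printed. The other three rows agree as well. They do not depend on the data source.

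Let E of N subjects truly meet the primary endpoint, and let s be the share of E who qualify by a form grade of 3 or 4 alone (no acuity loss, no CU/CP). A query on an AE log kept as instructed would report

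E × (1 − s) / N.

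The documents do not give s or the expected rate. Purely to show the range, take N = 40 (subjects enrolled, SAP 4.0) and E = 16 (40%, one row of Table 6):

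| s (assumed) | Reported | Exact 95% CI |
|---|---|---|
| 0 | 16/40 = 40.0% | 24.9 to 56.7 |
| 25% | 12/40 = 30.0% | 16.6 to 46.5 |
| 50% | 8/40 = 20.0% | 9.1 to 35.6 |
| 75% | 4/40 = 10.0% | 2.8 to 23.7 |

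These rows are not estimates. If the programming reads the form, the reported figure is E/N whatever s is.

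For time to any CEAE, Protocol 4.2 cites ocular side effects in more than 80% of patients, and Protocol 2.2 cites corneal events in 94.7% of the depatuxizumab mafodotin arm of the phase 3 trial. On 40 subjects that is about 32 (0.80 × 40) to 38 (0.947 × 40 = 37.9). Those rates come from other studies and are not limited to 8 weeks, so they show only that such events are common.

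**The case against.** The strongest reply is that the intended scale is clear. SAP 5.3.1 names it, SAP 11.2 uses the same acronym and does not mention CTCAE, SAP 5.2.1 refers to CEAE assessments, and the SAP's activity schedule lists them. There is also a possible route to coding: Protocol 6.1 has these events reported under the single term corneal epitheliopathy, and Protocol 4.1 lists AE reports among the ways of monitoring ocular side effects. The sponsor may code the form entries and run the CMQ on them. This stands in part. The documents do not exclude it, and results would then be unaffected. But they do not state it either, and a SAP written to guide programming should not leave its definition and its analysis rule at odds.

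Three stronger readings are tempting and not supported:

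- A reader might infer that the reported primary rate will be too low by some stated amount. That needs the query to run on the AE log alone and a value for s. The first is an inference and the second is not given.
- A reader might infer spurious differences between arms, from sites that log corneal terms despite the instruction. Nothing in the documents gives a misfiling rate. Subjects are randomized 1:1:1, so site habits need not line up with arm.
- A reader might infer from Appendix H that the form cannot supply onset times, because no start date is printed. The appendix shows response items only. It prints no visit date or subject number either, and any eCRF must hold both.

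It is also fair that the primary analysis is descriptive, in a study stopped at 40 subjects, and that a corneal analysis with almost no events would be noticed. A partly filled one might not be.

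**Conclusion.** The SAP is wrong as written on this point. Its operational rule (CMQ in 11.2; CTCAE grade and SOC/PT in 11.4) does not match its own definition in 5.3.1, or the way the Operations Manual has the data recorded and graded. The effect on results is conditional. Run on the AE log alone, the rule would drop Grade 3 and 4 events from component (b), and Grade 1 to 4 events from time to first CEAE, wherever they stand only on the form. The size cannot be derived from the documents, and there is no effect if the form is already read.

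The conclusion rests on one assumption, that the CMQ is a query on MedDRA-coded AE terms. The CTCAE conflict in 11.4 does not depend on it. The correction is cheap and concerns the primary endpoint, so it should be made.

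**What to change.** **SAP 11.2, component (b).** State that it is met by an overall CEAE grade of 3, 4 or 5 on the CEAE eCRF (Operations Manual Appendix H) at any assessment after the first Depatux-M dose, within 8 weeks and before BCL is placed. An assessment that triggers BCL on the same day counts; Operations Manual 3.5 has the lens placed at the visit where the criterion is met. CU/CP in the AE/SAE log counts as Grade 5.

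**SAP 11.2, time to first CEAE and to Grade 3 or higher.** Measure from the first Depatux-M dose to the first post-dose CEAE assessment with grade 1 or higher (3 or higher) that is worse than the pre-dose Week 1 Day 1 grade. The comparison is needed because CEAE is assessed on Week 1 Day 1, and Operations Manual 3.14 places the first dose after that day's other procedures. Without it, existing symptoms would count as Day 1 events.

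**SAP 11.4.** Replace CTCAE grade by CEAE grade for CEAEs, and tabulate the highest CEAE grade by arm. Keep CMQ 80000184 for a supplementary table of corneal terms in the AE log. That table should include events reported after subjects switch to the Protocol Appendix E schedule, which keeps AE assessment but has no CEAE assessment.

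**Cost.** A few sentences before database lock and no new data. Visit dates stand in for onset dates, and the main CEAE grade table loses its SOC/PT split.

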3.5 Ophthalmology Exam

Qualified medical personnel will perform the ophthalmologic examination as outlined in Section 2.1, Section 2.2, and Appendix C. Additional exams may be performed as clinically indicated.

Ophthalmology exams are to be performed 7 to 14 days after the 2nd and 3rd infusions of Depatux-M and must be completed prior to the next infusion of Depatux-M. Exams will at a minimum include assessment of visual acuity (as described below, using LogMAR scale and Appendix D), intraocular pressure, and slit lamp examination, as well as assessment for symptoms of eye pain and photophobia, and results will be recorded in the corresponding CRF (Appendix C).

Visual Acuity (VA) and Best corrected visual acuity (BCVA)

Instructions for obtaining visual acuity assessments at each ophthalmology visit (including the visual correction to be used for VA assessments, when BCL should be in place during VA assessment, and when manifest refraction is to be performed to assess BCVA) are described below. Visual acuity will be measured using the LogMAR scale in all cases. Visual acuity will be captured with baseline glasses (VAcc) or without glasses (VAsc) if the subject does not require correction at baseline during all ophthalmology visits. Best Corrected Visual Acuity (BCVA) will be assessed with manifest refraction during specified visits outlined in the protocol.

Baseline Ophthalmic Examination

- VA with baseline correction (cc or sc) *without BCL* – OD, OS, OU
 - Record glasses prescription if applicable
 - Record without glasses if subject does not require correction at baseline
 - *The same prescription will be used to measure VA (cc or sc) for all post-baseline visits*
- BCVA (with manifest refraction) – OD, OS, OU will be recorded

Post-baseline visits (prior to BCL intervention)

- VA with baseline correction (cc or sc) *without BCL* – OD, OS, OU
- *If VA OU (cc or sc) has declined ≥ 0.3 LogMAR from baseline OR if CEAE Grade ≥ 3 , place BCL and obtain the following:*
 - VA with baseline correction (cc or sc) *with BCL* – OD, OS, OU
 - BCVA (manifest refraction) *with BCL* – OD, OS, OU

Post-baseline visits (if BCLs are being used)

- VA with baseline correction (cc or sc) *without BCL* – OD, OS, OU – omit if BCL is not changed at the visit
- VA with baseline correction (cc or sc) *with BCL* – OD, OS, OU
- *If VA OU (cc or sc) with BCL decline ≥ 0.3 LogMAR from baseline remains, obtain the following:*

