APPENDIX D. VISUAL ACUITY EVALUATIONS FOR OPHTHALMOLOGY VISITS

Baseline

 ○ VA with baseline correction (cc or sc) without BCL – OD, OS, OU 
 ▪ Record glasses prescription if applicable ▪ Record without glasses if subject does not require correction at baseline ▪ The same prescription will be used to measure VA (cc or sc) for all post-baseline visits ○ BCVA (with manifest refraction) OD, OS, and OU will be recorded
Post-baseline visits (prior to BCL intervention)

 • VA with baseline correction (cc or sc) without BCL – OD, OS, OU • If VA OU (cc or sc) declined ≥ 0.3 LogMAR from baseline OR if CEAE Grade ≥ 3, place BCL and obtain the following: 
 ○ VA with baseline correction (cc or sc) with BCL – OD, OS, OU ○ BCVA (manifest refraction) with BCL – OD, OS, OU
Post-baseline visits (if BCLs are being used)

 • VA with baseline correction (cc or sc) without BCL – OD, OS, OU – omit if BCL is not changed at the visit • VA with baseline correction (cc or sc) with BCL – OD, OS, OU • If VA OU (cc or sc) with BCL decline ≥ 0.3 LogMAR from baseline remains, obtain the following: 
 ○ BCVA (manifest refraction) over BCL – OD, OS, OU – repeat every ~8 weeks
Post-baseline visits (if BCL intervention not tolerated)

 • VA with baseline correction (cc or sc) without BCL – OD, OS, OU • If VA OU (cc or sc) without BCL decline ≥ 0.3 LogMAR from baseline remains, obtain the following: 
 ○ BCVA (manifest refraction) without BCL – OD, OS, OU – repeat every ~8 weeks

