7.2 Dealing with Multiple Values on the Same Day

In cases multiple values are collected on the same day at baseline or post-baseline visit the worst value will be used for further analyses.

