11.3 Analysis of Secondary Endpoints

The maximum change from baseline in visual acuity on baseline corrected LogMAR scale prior to BCL intervention will be summarized by treatment arms and in overall population.

Kaplan-Meier plot for Time to BCL intervention will be produced. Time to BCL is defined as time from the randomization to the start date of BCL (as recorded in "Study Drug Administration - Bandage contact lens" CRF page). For subjects did not use BCL will be right-censored on the last assessment date.

In addition, Time to either $\geq +0.3$ change on LogMAR scale in baseline adjusted visual acuity or grade 3 or higher CEAE prior to BCL intervention will also be analyzed. For this analysis, $+0.3$ change on LogMAR scale in baseline adjusted visual acuity before the start date of BCL or grade 3 or higher CEAE prior to the start date of BCL intervention will be considered as events. If a patient receives BCL intervention without experiencing any one of these two events will also be considered as event on the start date of BCL

intervention. If a patient neither receives BCL intervention nor experiences any one of these two events, his/her time will be right-censored on the last assessment date.

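### Does the primary percentage lose subjects whose trigger falls on the day the bandage contact lens is started?

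*SAP*

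**What the plan says.** - **Endpoint definition.** Protocol 3.2 and SAP 5.3.1 define the primary endpoint over 8 weeks from the first dose of depatuxizumab mafodotin. A subject counts with a LogMAR worsening of at least 0.3 or a CEAE grade of 3 or more. Neither section mentions the lens.
- **Primary analysis.** SAP 11.2 adds a limit: events count "anytime over 8 weeks after initiation of Depatux-M and prior to BCL intervention will be summarized by treatment arms and in overall population". Protocol 3.3, which has prophylaxis and lens intervention assessed separately, supports that limit.
- **Post-lens repeat.** SAP 11.2 repeats the analysis in subjects who received the lens; there "baseline will be re-set to the last assessment prior to start of BCL intervention".
- **Time-to-event analysis.** For one specific analysis, SAP 11.3 counts "visual acuity before the start date of BCL or grade 3 or higher CEAE prior to the start date of BCL intervention". It adds a catch-all: "If a patient receives BCL intervention without experiencing any one of these two events will also be considered as event", dated to the lens start.
- **Same-day values.** SAP 7.2: where "multiple values are collected on the same day at baseline or post-baseline visit the worst value will be used for further analyses".
- **Exam procedure.** Operations Manual 3.5 and Appendix D, under a heading that begins "Post-baseline visits (prior to BCL intervention", call for acuity without the lens. If the criterion is met, the site is to "place BCL and obtain the following" (acuity with the lens). At later visits the no-lens acuity is marked "omit if BCL is not changed at the visit".
- **Form.** Operations Manual Appendix C has separate blocks for acuity without and with the lens. SAP 11.3 takes the lens start date from its own CRF page.

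**The concern.** The criterion that defines the primary endpoint is also the criterion for placing the lens, and the lens is to be placed at the visit that finds it. The trigger and the lens start will therefore often carry the same date, so the same-day case is a common one. SAP 11.2 is silent on it, while the next section renders the same idea as strictly before the start date. A programmer who reused the 11.3 flag in 11.2 and left out the catch-all would remove the assessments that prompted the change in management, which is what the primary objective asks about. SAP 11.3 would still count those subjects, so two analyses of one composite would disagree for a coding reason.

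The post-lens repeat could also be affected. Its re-set baseline would fall back to an earlier visit. The worst-value rule in SAP 7.2 might then let a no-lens reading count as a failure of the lens.

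**Working it through.** **1. The plan's own precision figures.** Protocol Table 6 uses n = 30 per arm. The normal-approximation interval, p ± 1.96 × √(p(1 − p)/n), reproduces all four rows. For 12/30: 0.40 ± 1.96 × √(0.40 × 0.60/30) = 0.40 ± 0.175, or 22.5% to 57.5%, as printed. These figures do not depend on how same-day assessments are classed.

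**2. Which reading the documents support.**

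| Source | Bearing on a same-day trigger |
|---|---|
| SAP 11.2 | Refers to the intervention, not to its start date |
| SAP 11.3 | Uses the start date, but only for its own time-to-event analysis, and keeps same-day cases through the catch-all |
| Operations Manual 3.5, Appendix D | List the trigger visit's no-lens acuity, and the CEAE grade as a ground for placement, in the pre-lens block |
| Protocol 5.7 | The subject meets the criterion and then receives the lens |
| Operations Manual Appendix C | No-lens and with-lens acuity are separate fields, so their order can be recovered within one date |

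All but the 11.3 wording place the trigger before the lens, and 11.3 does not govern 11.2. On this reading the loss is zero.

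**3. Size if the 11.3 date rule were carried over without its catch-all.** Let s be the share of subjects with an event whose only qualifying assessment is on the lens start date. The documents do not give s; 0 to 100% is an assumed range. The percentage becomes x(1 − s)/n. For the 12/30 row:

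| s | Percentage |
|---|---|
| 0% | 40.0 |
| 25% | 30.0 |
| 50% | 20.0 (95% CI 5.7 to 34.3) |
| 75% | 10.0 |
| 100% | 0.0 |

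Both components are exposed. SAP 11.3 applies its date rule to CEAE grades as well as acuity, and Operations Manual 2.1 schedules both at the Week 3, 5 and 7 visits (Week 9 is a CEAE telephone call). This table shows what an assumed share would do; it is not evidence that any subject is affected.

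**4. Scale at actual enrolment.** SAP 4.0 gives 40 subjects; 40/3 = 13.3 per arm if the split is even. One subject is 1/13 = 7.7 points in an arm and 1/40 = 2.5 points overall. With illustrative counts and exact (Clopper-Pearson) 95% intervals:

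- 5/13 = 38.5% (13.9 to 68.4)
- 4/13 = 30.8% (9.1 to 61.4)

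The shift from one subject is small beside either interval.

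**5. The post-lens repeat.** All LogMAR values here are hypothetical.

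- *Date reading only.* The placement-day no-lens value is compared with the previous visit. 0.3 − 0.0 = +0.3 would be a failure; 0.3 − 0.1 = +0.2 would not.
- *Lens-change visit.* Take a re-set baseline of 0.4, no-lens 0.7 and with-lens 0.3. Pooling under the worst-value rule gives 0.7 − 0.4 = +0.3 (failure); the with-lens value gives 0.3 − 0.4 = −0.1 (no failure).

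The second result needs SAP 7.2 to pool two different form fields. By the same logic it would pool right eye, left eye, both eyes and best-corrected acuity, which nobody would program. Operations Manual 3.5 already checks the both-eyes acuity with the lens in place against the 0.3 threshold once lenses are worn.

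**The case for a change.** The strongest reply is that, in a trial whose primary result is an estimate, the figure should not hang on a choice between *before* and *on or before*. The exam form has one exam date and a clock time only for intraocular pressure, so dates alone cannot order the trigger and the lens. The one place where the SAP writes the idea in dates points the wrong way. The CEAE outputs without a lens cut-off (the Kaplan-Meier analysis in 11.2 and the tables in 11.4) do not show subjects who triggered on acuity alone. A clarifying sentence would need no new data.

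Part of this stands: SAP 11.2 has no sentence on the point, and SAP 7.2 does not mention lens status. What does not stand is the step from silence to loss. That step needs half of a rule to be moved out of the analysis it was written for, and the result would remove the event that defines the endpoint. The 11.3 composite, which retains same-day cases, would expose the mismatch.

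A fuller rule also needs care. Using only with-lens acuity after placement would leave subjects who cannot tolerate the lens without a usable reading. Operations Manual 3.5 provides only no-lens acuity for them, yet they remain in the post-lens denominator.

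**Conclusion.** No change to the plan is needed. This is a gap that an analyst working from the SAP and the Operations Manual would fill sensibly: no-lens acuity and CEAE grades from the placement visit are pre-lens, that visit's no-lens acuity is the re-set baseline, and the worst-value rule works within one kind of measurement. On that reading no subject leaves the primary percentage.

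The possible harm is conditional on a misreading, and its size cannot be derived from the documents. The figure of 7.7 points per reclassified subject assumes an even split of the 40 enrolled, and the event counts are illustrative. The setting also limits what is at stake: the study is exploratory, its primary objective is estimation by arm, enrolment has stopped, and the intervals at about 13 per arm are far wider than a one-subject shift. Stating the convention in the programming specification or a table footnote would be good housekeeping, but the plan is workable without it.
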